			
 
GUILLAIN-BARRE:
 
It is important to consider here that the use of steroids as the primary treatment of Guillain-Barre is not typically considered effective.
 

Adverse Events	Severity Grade of the Event (NCI CTCAE	Dose Modifications	Toxicity Management
	version 4.03)		
 
Patients requiring treatment should be started with IV IG and followed by plasmapheresis if not responsive to IV IG.
 

<sup>a ASCO Educational Book 2015 "Managing Immune Checkpoint Blocking Antibody Side Effects" by Michael Postow MD.

AChE Acetylcholine esterase; ADL Activities of daily living; AE Adverse event; ALP Alkaline phosphatase test; ALT Alanine aminotransferase; AST Aspartate aminotransferase; BUN Blood urea nitrogen; CT Computed tomography; CTCAE Common Terminology Criteria for Adverse Events; ILD Interstitial lung disease; irAE Immune-related adverse event; IG Immunoglobulin; IV Intravenous; GI Gastrointestinal; LFT Liver function tests; LLN Lower limit of normal; MRI Magnetic resonance imaging; NCI National Cancer Institute; NCCN National Comprehensive Cancer Network; PCP; PO By mouth; T3 Triiodothyronine; T4 Thyroxine; TB Total bilirubin; TNF Tumor necrosis factor; TSH Thyroid-stimulating hormone; ULN Upper limit of normal.

b FDA Liver Guidance Document 2009 Guidance for Industry: Drug Induced Liver Injury – Premarketing Clinical Evaluation.

Severity Grade of the Event (NCI CTCAE version 4.03)	Dose Modifications	Toxicity Management
Any Grade	General Guidance	For Any Grade:  - Manage per institutional standard at the discretion of investigator.  - Monitor patients for signs and symptoms of infusion-related reactions (eg, fever and/or shaking chills, flushing and/or itching, alterations in heart rate and blood pressure, dyspnea or chest discomfort, or skin rashes) and anaphylaxis (eg, generalized urticaria, angioedema, wheezing, hypotension, ortachycardia).
Grade 1 or 2	For Grade 1:  The infusion rate of study drug/study regimen may be decreased by 50% or temporarily interrupted until resolution of the event.	
 
For Grade 1 or 2:
 
Acetaminophen and/or antihistamines may be administered per institutional standard at the discretion of theinvestigator.
 
Consider premedication per institutional standard prior to subsequent doses.
 

	For Grade 2:  The infusion rate of study drug/study regimen may be decreased 50% or temporarily interrupted until resolution of theevent.  Subsequent infusions may be given at 50% of the initial infusion rate.	
 
Steroids should not be used for routine premedication of Grade ≤ infusion reactions.
 

Grade 3 or 4	For Grade 3 or 4:  Permanently discontinue study drug/study regimen.	For Grade 3 or 4:  - Manage severe infusion-related reactions per institutional standards (eg, IM epinephrine, followed by IV diphenhydramine and ranitidine, and IV glucocorticoid).

CTCAE Common Terminology Criteria for Adverse Events; IM Intramuscular; IV Intravenous; NCI National Cancer Institute.

Severity Grade of the Event (NCI CTCAE version 4.03)	Dose Modifications	Toxicity Management  Treat accordingly, as per institutional standard.		
Any Grade	Note: Dose modifications are not required for AEs not deemed to be related to study treatment (ie, events due to underlying disease) or for laboratory abnormalities not deemed to be clinically significant.			
Grade 1 No dose modifications.		Treat accordingly, as per institutional standard.		
Grade 2	Hold study drug/study regimen until resolution to ≤Grade 1 or baseline.	Treat accordingly, as per institutional standard.		
Grade 3	Hold study drug/study regimen until resolution to ≤Grade 1 or baseline.	Treat accordingly, as per institutional standard.		
	For AEs that downgrade to ≤Grade 2 within 7 days or resolve to ≤Grade 1 or baseline within 14 days, resume study drug/study regimen administration. Otherwise, discontinue study drug/study regimen.			
Grade 4	Discontinue study drug/study regimen (Note: For Grade 4labs, decision to discontinue should be based on accompanying clinical signs/symptoms, the Investigator's clinical judgment, and consultation with the Sponsor.).	Treat accordingly, as per institutional standard.		

Note: As applicable, for early phase studies, the following sentence may be added: "Any event greater than or equal to Grade 2, please discuss with Study Physician." AE Adverse event; CTCAE Common Terminology Criteria for Adverse Events; NCI National Cancer Institute.

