#### Dose Modifications

Drug administration modifications of study drug/study regimen will be madeto manage potential immune-related AEs based on severity of treatment-emergent toxicities graded per NCI CTCAE v4.03.

In addition to the criteria for permanent discontinuation of study drug/study regimen based on CTC grade/severity (table below), permanently discontinue study drug/study regimen for the following conditions:

- Inability to reduce corticosteroid to a dose of ≤10 mg of prednisone per day (or equivalent) within 12 weeks after last dose of study drug/study regimen
- Recurrence of a previously experienced Grade 3 treatment-relatedAE following resumption of dosing

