Adverse Events	Severity Grade of the Event (NCI CTCAE	Dose Modifications	Toxicity Management
	version 4.03)		
		For elevations in transaminases	
		>8 × ULN or elevations in bilirubin $>$ 5 ×	
		ULN, discontinue study drug/study	
		regimen.	
		Permanently discontinue study	
		drug/study regimen for any case meeting	
		Hy's law criteria (AST and/or ALT $>$ 3 $\times$	
		ULN + bilirubin >2 × ULN without	
		initial findings of cholestasis (ie, elevated	
		alkaline P04) and in the absence of any	
		alternative cause. b	
		For Grade 4:	
		Permanently discontinue study	
		drug/study regimen.	
Nephritis or renal	Any Grade	General Guidance	For Any Grade:
dysfunction			
 
Consult with nephrologist.
 

(elevated serum creatinine)			
 
Monitor for signs and symptoms that may be related to changes in renal function (eg, routine urinalysis, elevated serum BUN and creatinine, decreased creatinine clearance, electrolyte imbalance, decrease in urine output, or proteinuria).
 

			
 
Patients should be thoroughly evaluated to rule out any alternative etiology (eg, disease progression orinfections).
 

			
 
Steroids should be considered in the absence of clear alternative etiology even for low-grade events (Grade 2), in order to prevent potential progression to higher grade event.
 

	Grade 1	No dose modifications.	For Grade 1:

Adverse Events	Severity Grade of the Event (NCI CTCAE version 4.03)	Dose Modifications	Toxicity Management
	(Serum creatinine > 1 to 1.5 × baseline; > ULN to 1.5 × ULN)  Grade 2 (serum creatinine >1.5 to 3.0 × baseline; >1.5 to 3.0 × ULN)	Hold study drug/study regimen until resolution to Grade ≤1 or baseline.  If toxicity worsens, then treat as Grade 3 or 4.  If toxicity improves to Grade ≤1 or baseline, then resume study	
 
Monitor serum creatinine weekly and anyaccompanying symptoms.
 
If creatinine returns to baseline, resume its regular monitoring per study protocol.
 
If creatinine worsens, depending on the severity, treat as Grade 2, 3, or 4.
 
Consider symptomatic treatment, including hydration, electrolyte replacement, and diuretics.
 
For Grade 2:
 
Consider symptomatic treatment, including hydration, electrolyte replacement, and diuretics.
 
Carefully monitor serum creatinine every 2 to 3 days and as clinically warranted.
 
Consult nephrologist and consider renal biopsy if clinically
 

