# 10.5.2 Hepatic function abnormality/Hy's Law

Cases where a patient shows elevations in liver biochemistry may require further evaluation and occurrences of AST or ALT  $\ge 3 \times \text{ULN}$  together with total bilirubin  $\ge 2 \times \text{ULN}$  may need to be reported as SAEs. Hepatic function abnormality (as defined in Section 10.1.3.) in a study subject, with or without associated clinical manifestations, is required to be reported as "hepatic function abnormal" within 24 hours of knowledge of the event to the sponsor and AstraZeneca/MedImmune Patient Safety using the designated Safety e-mailbox (for contact information), unless a definitive underlying diagnosis for the abnormality (e.g., cholelithiasis or bile duct obstruction) that is unrelated to investigational product has been confirmed.

- If the definitive underlying diagnosis for the abnormality has been established and is unrelated to investigational product, the decision to continue dosing of the study subject will be based on the clinical judgment of the investigator.
- If no definitive underlying diagnosis for the abnormality is established, dosing of the study subject must be interrupted immediately. Follow-up investigations and inquiries must be initiated by the investigational site without delay.

Each reported event of hepatic function abnormality will be followed by the investigator and evaluated by the sponsor and AstraZeneca/MedImmune.

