**Definitions** 

# Potential Hy's Law (PHL)

Aspartate Aminotransferase (AST) or Alanine Aminotransferase (ALT)  $\geq$ 3 × Upper Limit of Normal (ULN) **together with** Total Bilirubin (TBL)  $\geq$ 2 × ULN at any point during the study following the start of study medication, irrespective of an increase in Alkaline Phosphatase (ALP).

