# Hy's Law (HL)

AST or ALT  $\ge 3 \times$  ULN **together with** TBL  $\ge 2 \times$  ULN, where no other reason, other than the IMP, can be found to explain the combination of increases, eg, elevated ALP indicating cholestasis, viral hepatitis, another drug.

For PHL and HL, the elevation in transaminases must precede or be coincident with (ie, on the same day) the elevation in TBL, but there is no specified timeframe within which the elevations in transaminases and TBL must occur.

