# Review and Assessment of Potential Hy's Law Cases

The instructions in this Section should be followed for all cases where PHL criteria are met.

• No later than 3 weeks after the biochemistry abnormality was initially detected, the Study Physician contacts the Investigator in order to review available data and agree on whether there is an alternative explanation for meeting PHL criteria other than DILI caused by the

IMP. The AstraZeneca Medical Science Director and Global Safety Physician will also be involved in this review together with other subject matter experts as appropriate.

According to the outcome of the review and assessment, the Investigator will follow the instructions below.

If there is an agreed alternative explanation for the ALT or AST and TBL elevations, a determination of whether the alternative explanation is an AE will be made and subsequently whether the AE meets the criteria for a SAE:

- If the alternative explanation is **not** an AE, record the alternative explanation on the appropriate eCRF.
- If the alternative explanation is an AE/SAE, record the AE /SAE in the eCRF accordingly and follow the AZ standard processes.

If it is agreed that there is **no** explanation that would explain the ALT or AST and TBL elevations other than the IMP:

- Report an SAE (report term "Hy's Law") according to AstraZeneca standard processes.
  - The "Medically Important" serious criterion should be used if no other serious criteria apply.
  - As there is no alternative explanation for the HL case, a causality assessment of "related" should be assigned.

If there is an unavoidable delay of over 3 weeks in obtaining the information necessary to assess whether or not the case meets the criteria for HL, then it is assumed that there is no alternative explanation until such time as an informed decision can be made:

- Report an SAE (report term "Potential Hy's Law"), applying serious criteria and causality assessment as per above.
- Continue follow-up and review according to agreed plan. Once the necessary supplementary information is obtained, repeat the review and assessment to determine whether HL criteria are met. Update the SAE report according to the outcome of the review.

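### Read literally, Table 3's permanent stop for Hy's-law liver injury exempts any man with raised ALP at onset; Appendix 1 does not, leaving a narrow gap at Grade 2 and quickly recovering Grade 3

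*Combined protocol and SAP*

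**What the plan says.** Three parts of the protocol deal with combined rises in transaminases and bilirubin.

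- **Section 10.1.2, Table 3, Hepatitis row.** Study drug is stopped permanently when AST and/or ALT exceeds 3 × ULN with bilirubin above 2 × ULN, on two conditions. There must be no "initial findings of cholestasis (ie, elevated" alkaline phosphatase), and there must be no alternative cause. The same row gives hold-and-resume rules by grade. Table 3's general instructions add that sites should "permanently discontinue study drug/study regimen for the following conditions" and list two: steroid that cannot be brought down to 10 mg prednisone a day within 12 weeks of the last dose, and "Recurrence of a previously experienced Grade 3 treatment-relatedAE following resumption of dosing".
- **Appendix 1.** Potential Hy's Law is defined "irrespective of an increase in Alkaline Phosphatase (ALP"). It becomes Hy's Law when no reason other than the study drug "can be found to explain the combination of increases, eg, elevated ALP indicating cholestasis", viral hepatitis or another drug. For such a case the appendix says: "As there is no alternative explanation for the HL case, a causality assessment of" related is to be given. On timing: "No later than 3 weeks after the biochemistry abnormality was initially detected, the Study Physician contacts the Investigator in order to review available data". The appendix describes itself as a process for identifying and reporting cases, not a full management guide. It orders no dose stop.
- **Section 10.5.2.** There is no ALP condition. "If the definitive underlying diagnosis for the abnormality has been established and is unrelated to investigational product, the decision to continue dosing" rests on the investigator's clinical judgment. Where no such diagnosis is found, dosing is interrupted at once. The section gives neither a restart condition nor a permanent stop.

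Section 4.3 item 4 takes its mandatory stops from Table 3, and Section 10.1.1 also sends management of hepatic abnormality there. Table 3 therefore governs dosing.

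**The concern.** In Table 3 the abbreviation for *that is* makes raised ALP the definition of cholestasis. The line sets no ALP threshold, names no source and does not require that the ALP explain the event. Absence of another cause is a separate condition. Taken at its word, a raised ALP at onset removes the case from the rule. In Appendix 1, ALP counts only as an explanation.

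The difference matters in this population. Section 4.1 item 10 requires bone metastases in every man, and the eligibility list sets no ALP limit. Bone disease can raise ALP with no cholestasis; that is general clinical knowledge and is not stated in the documents. A man could have bone-derived ALP, develop Hy's-law values, be adjudicated under Appendix 1 as having drug-related Hy's Law, and still be managed under wording that lets treatment resume. At stake is re-exposure of a patient to a drug judged to have injured his liver.

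**Working it through.** No sample size, power or event figure bears on this, so the check is to sort the Hy's-law range into Table 3's own bands and see which cases would lack a mandatory stop if raised ALP took them out of the Hy's-law line.

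**Inputs.** Table 3, Hepatitis row, in multiples of ULN:
- Grade 2: ALT/AST >3–5 and/or bilirubin >1.5–3.
- Grade 3: ALT/AST >5–20 and/or bilirubin >3–10.
- Grade 4: ALT/AST >20 and/or bilirubin >10.
- Within Grade 3, the hold rule runs up to 8 (transaminases) or 5 (bilirubin); above either, discontinue.

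The Hy's-law range starts above 3 and above 2.

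| ALT/AST | Bilirubin >2–3 | >3–5 | >5–10 | >10 |
|---|---|---|---|---|
| >3–5 | Grade 2: hold, resume | Grade 3: hold, 14-day limit | discontinue | Grade 4: permanent stop |
| >5–8 | Grade 3: hold, 14-day limit | Grade 3: hold, 14-day limit | discontinue | Grade 4: permanent stop |
| >8–20 | discontinue | discontinue | discontinue | Grade 4: permanent stop |
| >20 | Grade 4: permanent stop | Grade 4: permanent stop | Grade 4: permanent stop | Grade 4: permanent stop |

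**Counts.** There are 4 × 4 = 16 cells.
- Grade 4: 4 + 4 − 1 = 7 cells.
- Discontinue below Grade 4: 5 cells. The word for permanent is not printed there. The hold line joins its two limits with *or*, so a case over one limit and under the other meets both instructions; I applied the stricter.
- Stopped whatever the ALP: 7 + 5 = 12 cells.
- Lower-band Grade 3: 3 cells, stopped permanently unless back to Grade 1 or below, or to baseline, inside 14 days.
- Grade 2: 1 cell, with no time-based stop.

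These are cells, not event frequencies.

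**Examples.** ALT 4 with bilirubin 2.5 is Grade 2: hold, then resume. ALT 7 with bilirubin 4 is Grade 3: hold, then resume if recovered within 14 days and after the steroid taper. ALT 9 with bilirubin 2.5 is discontinued.

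**General stops.** The 12-week steroid condition can apply to a first event in any cell. The recurrence condition applies only after dosing has resumed. Neither is triggered by a finding of Hy's Law.

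**Timing.** Count from detection as day 0. The Appendix 1 review is due by day 21. Where steroids are used, Table 3 asks for a taper of at least 28 days from the start of improvement.
- Improvement on day 0: earliest restart day 28, so 28 − 21 = 7 days after the review is due.
- Improvement on day 5: 5 + 28 = day 33.
- Improvement on day 14: 14 + 28 = day 42.

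The margin is not guaranteed. Appendix 1 allows for an unavoidable delay beyond 3 weeks, and its default then is an SAE report, not a dosing order. A Grade 2 case that settles before the 3-to-5-day steroid trigger has no taper, so Table 3's resume point can come before day 21.

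**The case against.** The strongest reply is that the texts agree. The operative words in Table 3 concern findings of cholestasis, and the parenthesis names its laboratory sign; ALP from bone is not such a finding. Table 3's footnote and Appendix 1 cite the same FDA liver guidance, which suggests one definition. Section 10.1.1 uses the same thresholds with no ALP condition and looks for objective evidence of another cause, such as bile duct obstruction.

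The other controls are also substantial. An adjudicated Hy's-law case has by definition no other explanation, so it stays in Section 10.5.2's interruption branch. Section 4.3 item 2 ends dosing if the investigator or sponsor considers further drug contraindicated. Appendix 1 brings in the Study Physician once the potential criteria are met, and Table 3 asks for a discussion with the study physician if a Grade 2 rise has not resolved in 1 to 2 days.

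Much of this stands. The harmonised reading is reasonable and the controls make a restart unlikely. But they either interrupt dosing without saying for how long or depend on judgment, while the plan chose a mandatory permanent stop for Hy's Law. The only written restart conditions are Table 3's, and the scope of the stop should not turn on a parenthesis.

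A reader might go further and infer that raised ALP takes a man out of every permanent stop. The documents do not support that: the severity, 14-day and steroid criteria above apply whatever the ALP.

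**Conclusion.** The point holds in a limited form. For a man with raised ALP at onset, no passage orders a permanent stop on Hy's-law grounds. A stop is mandatory only if a separate criterion is met: Grade 4; ALT/AST above 8 × or bilirubin above 5 × ULN; Grade 3 not recovered within 14 days; or steroid not reducible within 12 weeks. What remains is Grade 2 (ALT/AST >3–5 × with bilirubin >2–3 × ULN), and Grade 3 up to 8 × and 5 × that recovers within 14 days. Recovery while drug is held does not undo a judgment that the drug caused the injury.

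The number of men affected cannot be computed and is likely very small among at most 27. Entry limits (AST/ALT ≤2.5 × and bilirubin ≤1.5 × ULN, with an exception for Gilbert's syndrome) and the exclusion of liver metastases mean that Hy's-law values would generally have to arise on study. The conclusion rests on the literal reading of the parenthesis and on the outside fact that bone disease can raise ALP. It would be wrong to infer that the plan directs re-exposure after proven drug-induced injury, because Section 10.5.2 interrupts dosing. Severity is low, and no endpoint or analysis is affected.

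**What to change.** In Table 3's Hy's-law line, replace the parenthesis equating cholestasis with raised ALP by Appendix 1's test: raised ALP that indicates cholestasis and explains the combined rise. Add that any case adjudicated as Hy's Law under Appendix 1 is permanently discontinued at any grade, overriding the resume rules, and that drug stays on hold under Section 10.5.2 until that review is complete.

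The cost is a wording change in one row with two cross-references. Attribution of the ALP stays with a review that is already required, so the rule adds no test or visit. The downside is that an occasional man with ALP of mixed origin may be stopped permanently, and a mild Grade 2 case may wait about 3 weeks for the review, or longer if it is delayed.

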## 4.3 Withdrawal of Subjects from Study Treatment and/or Study

#### Permanent discontinuation of either durvalumab plus tremelimumab or durvalumab.

An individual subject will not receive any further investigational product if any of the following occur in the subject in question:

- 1. Withdrawal of consent or lost to follow-up.
- 2. Adverse event that, in the opinion of the investigator or the sponsor, contraindicates further dosing.
- 3. Subject is determined to have met one or more of the exclusion criteria for study participation at study entry and continuing investigational therapy might constitute a safety risk.
- 4. Any AE that meets criteria for discontinuation as defined in the Dosing Modification and Toxicity Management Guidelines (see Table 3).
- 5. Subject noncompliance that, in the opinion of the investigator or sponsor, warrants withdrawal; eg, refusal to adhere to scheduled visits.
- 6. Initiation of alternative anticancer therapy including another investigational agent.
- 7. Confirmation of PD and investigator determination that the subject is no longer benefiting from treatment with durvalumab + tremelimumab.
- 8. Withdrawal of consent from further treatment with IP. The patient is, at any time, free to discontinue treatment, without prejudice to further treatment. A patient who discontinues treatment is normally expected to continue to participate in the study unless they specifically withdraw their consent to further participation in any study procedures and assessments

Subjects who are permanently discontinued from further receipt of investigational product, regardless of the reason (withdrawal of consent, due to an AE, other), will be identified as having permanently discontinued treatment.

Subjects who are permanently discontinued from receiving investigational product will be followed for safety per Section 10.1 and Table 2, including the collection of any protocol-specified blood specimens, unless consent is withdrawn or the subject is lost to follow-up or enrolled in another clinical study. All subjects will be followed for survival. Subjects who decline to return to the site for evaluations will be offered follow-up by phone per the schedule in table 2 as an alternative.

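### Table 3, non-immune Grade 3 row: an event that falls to Grade 2 within 7 days and stays there is both to be held and to be resumed

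*Combined protocol and SAP*

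**What the plan says.** The last part of Table 3 covers non-immune-mediated reactions, one row per grade. The Grade 3 row has two instructions.

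- Line 1: "Hold study drug/study regimen until resolution to ≤Grade 1 or baseline". It carries no time limit.
- Line 2: "For AEs that downgrade to ≤Grade 2 within 7 days or resolve to ≤Grade 1 or baseline within 14 days", "resume study drug/study regimen administration". It then closes with "Otherwise, discontinue study drug/study regimen".

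The Grade 2 row has the same hold wording as line 1. The any-grade row exempts events judged unrelated to treatment and laboratory changes judged not clinically significant.

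Table 3 is operative. Section 4.3, item 4, lists among the reasons for permanent discontinuation: "Any AE that meets criteria for discontinuation as defined in the Dosing Modification and Toxicity Management Guidelines (see Table 3". Section 6.3.1 does not permit dose reductions, so the main decision after a toxicity is whether to hold, resume or discontinue. Both drugs are given every four weeks (Sections 3.1 and 6.2.1).

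**The concern.** Line 1 ends the hold at Grade 1 or baseline. The first limb of line 2 ends it at Grade 2, provided Grade 2 is reached within a week. Between those two thresholds the row points both ways, and the protocol has no sentence ranking one line above the other.

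Safety and tolerability is the only primary objective (Section 2.1), and the action taken with study drug is recorded for each adverse event (Section 10.2). Two investigators could each follow the protocol on the same event and record different actions.

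An early event can also decide whether a patient receives the two doses needed for evaluability (Sections 4.4 and 11.1.2) or the two combination cycles required before monotherapy (Section 6.2.1). Enrolment is capped at 27 to obtain 20 evaluable patients, which leaves room for 27 − 20 = 7 who are not evaluable, so single cases count.

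**Working it through.** The plan states no figure on this point, so there is none to reproduce. The check applies each line literally to every possible time course and compares the instructions.

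**Set-up.** Let t2 be the day on which a Grade 3 event first reaches Grade 2 or lower. Let t1 be the day on which it first reaches Grade 1 or baseline, with t1 ≥ t2. Each is a day from 1 to 30, or never.

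- Line 1: hold on every day before t1.
- Line 2: resume from t2 if t2 ≤ 7; resume from t1 if t1 ≤ 14; discontinue after day 14 if neither holds.

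This gives 31 + 30 + … + 2 + 1 = 496 time courses. They fall into three groups.

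| Time course | Line 1 | Line 2 | Courses |
|---|---|---|---|
| t2 ≤ 7 and t1 > t2 | hold until t1 | resume from t2 | 30 + 29 + 28 + 27 + 26 + 25 + 24 = 189 |
| t1 = t2 ≤ 7, or t2 > 7 with t1 ≤ 14 | hold ends at t1 | resume from t1 | 7 + 28 = 35 |
| t2 > 7 and t1 > 14 | hold until t1 | discontinue after day 14 | 240 + 24 + 8 = 272 |

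The counts only confirm that the groups are exhaustive (189 + 35 + 272 = 496). They are cells in a grid, not expected frequencies of events.

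**First group.** With Grade 2 on day 5 and Grade 1 on day 10, on day 20 or never, line 1 says hold from day 5 until Grade 1 is reached, and line 2 says resume from day 5. The discontinuation clause is never reached, because the first limb of line 2 is already met. If the event is now treated as Grade 2, the Grade 2 row also says hold. The conflict disappears only if Grade 2 is the patient's own baseline.

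**Second group.** With Grade 2 and Grade 1 both first met on day 5, or Grade 2 on day 10 and Grade 1 on day 12, both lines lead to resumption on the same day.

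**Third group.** With Grade 2 on day 10 and Grade 1 on day 20, line 1 alone would keep holding until day 20, and line 2 discontinues after day 14. These fit together if line 2 puts a 14-day limit on the hold.

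**All three outcomes.** No time course receives a resume instruction that conflicts with the hold and also a discontinue instruction.

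**When the first-group conflict alters treatment.** It does so only if a dose falls due between t2 and t1. Take t2 = 5 and t1 = 10, counting from onset. If onset is two days after an infusion (assumed), Grade 1 is reached 2 + 10 = 12 days after that infusion, well before the next dose at 28 days, and neither line costs a dose. If onset is five days before a due dose (assumed), line 2 allows that dose on the day, and line 1 defers it by 10 − 5 = 5 days. If the event stays at Grade 2, line 1 defers it with no end date.

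**The case against.** The best defence is that line 2 is the more specific instruction. Line 1 states the default and line 2 the terms on which a Grade 3 hold ends, so the row can be followed in sequence. Because rows are keyed to the severity of the event, the Grade 2 row need not govern a Grade 3 event that has since improved. The row is also narrow: unrelated events are exempt, and Table 3 treats events without a clear alternative cause as potentially immune related, which sends many to other rows.

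Much of this limits the point. The Grade 2 row adds ambiguity but does not by itself make the contradiction, and the row's reach is small. The sequence argument does not remove the conflict. Line 1 says in terms that the hold lasts until Grade 1 or baseline, and line 2 ends it at a different grade without being marked as an exception. Comparable rows use one threshold for the hold and for its time limit: Grade 3 hepatitis within the stated liver-test limits (14 days), and Grade 3 rash, neurotoxicity and neuromotor syndromes (30 days). Here the thresholds differ.

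Those same rows defeat a stronger reading. A reader might infer that an event reaching Grade 1 on day 20 is resumed under line 1 and discontinued under line 2. If it had reached Grade 2 by day 7, line 2 says resume. If not, line 2 is the ordinary time limit on a hold used elsewhere in the table. Line 1 never says to resume on day 20.

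**Conclusion.** The point stands in a narrow form. Line 1 of the Grade 3 row conflicts with the first limb of line 2 for an event that is treatment-related, falls to Grade 2 by day 7, remains there above the patient's baseline, and is still at that grade when a dose is due. This rests on a literal reading of the row and on the absence of any sentence giving one line precedence.

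A reader might go further and infer that one and the same event can be held, resumed or discontinued. The documents do not support that: the two resumption conditions are joined by an *or*, so an event that meets the first never reaches the discontinuation clause. Nor is every Grade 3 non-immune event affected. Those in the second group get one consistent instruction, and those in the third can be read consistently.

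No statistical figure moves. TOX depends on grade, attribution, the first 8 weeks and the response to steroids (Section 11.2.1), not on whether drug was held, and the safety set needs only one dose (Section 11.1.1). The documents give no frequency for the affected events. What remains is contradictory instruction on re-exposure after a Grade 3 event, with possible effects on recorded exposure, discontinuations and, in individual cases, evaluability.

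**What to change.** The sponsor should reconcile three pieces of Table 3: the Grade 3 hold line, the Grade 3 clause on reaching Grade 2 within 7 days, and the Grade 2 row as it applies to an event that began at Grade 3. After reconciliation, each combination of grade and time should lead to a single action. Which rule is right is for the sponsor to decide, and no rule is proposed here.

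The consent-waiver text in Section 8.2.2 says that patients have completed the treatment phase. For events already managed, the report should therefore state which line was applied wherever exposure and discontinuations are presented.

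The cost is a wording change in one part of one table and a short statement in the report. No sample size, TOX definition or monitoring table needs to be recalculated.
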